#### 4.5.2 Treatment Assignments

The factors defined in Section 4.5.1 will be used as stratification factors.

After the patient has been registered into the study, the values of the stratification factors will be recorded, and the patient will be assigned to one of the following treatment groups using the Pocock and Simon dynamic allocation procedure [41] which balances the marginal distributions of the stratification factors between the treatment groups.

- Oxybutynin: 2.5 mL oral BID Days 8 through 49 (total of 42 days)
- Oxybutynin: 5 mL oral BID Days 8 through 49 (total of 42 days)
- Placebo: 2.5 mL oral BID Days 8 through 49 (total of 42 days)
- Placebo: 5 mL oral BID Days 8 through 49 (total of 42 days)

Note: Oxybutynin concentration = 1mg/mL.

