#### 11.1 Baseline Symptom Determination (Appendix II)

The baseline symptoms determination is completed after registration and randomization but prior to initiation of study treatment. This form has patients record the number of total hot flashes they experience on a daily basis, along with the number of hot flashes according to severity (mild, moderate, severe, or very severe) over the first 7 days of the study period. It is estimated that completing the baseline symptom determination will take 3-5 minutes daily. Questionnaires should be returned to the investigator at the end of the baseline week (week 1) and at the end of treatment (i.e., after the 7th week following study entry). The patient should be supplied with two addressed/stamped envelopes for returning the forms.

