#### 13.4 Analysis Plan

**To assess efficacy**, a mixed model will be estimated that includes baseline and weekly hot flash scores across the 6-week treatment period. The mixed model will include a fixed intercept; fixed effect for time, arm, and arm by time interaction; and residual covariance matrix based on the observed covariances. Alternative structures will be investigated for the residual covariance matrix, with final selection based on convergence of the mixed model and minimization of the Akaike information criterion. Stratification factors used in the randomization as well as baseline patient characteristics and prognostic factors may be included in the mixed model as covariates if imbalances across arms occur. For this mixed model, time will be treated as nominal (not continuous), such that the mixed model will not be making assumptions about the trajectory of

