patients' hot flash scores over time. Estimates from the mixed model will be used to construct 90% confidence intervals for mean differences in hot flash score reduction from baseline to 6 weeks post-randomization between the oxybutynin and placebo arms (i.e., Arm A versus Arms C and D combined; Arm B versus Arms C and D combined). To control the Type I error rate, a fixed sequence procedure will be employed such that the following two tests will be sequenced rather than conducted simultaneously. Hot flash score reduction from baseline to 6 weeks will be compared across patients assigned to oxybutynin at 5.0 mL twice daily (Arm B) and patients assigned to placebo (Arms C and D combined) using a contrast estimated via the mixed model. The contrast will involve a two-sided t-test with a nominal significance level of  $\alpha = .10$ . If and only if this test is significant, hot flash score reduction from baseline to 6 weeks will be formally compared across patients assigned to oxybutynin at 2.5 mL twice daily (Arm A) and patients assigned to placebo (Arms C and D combined) using a second contrast estimated via the mixed model. This contrast will also involve a two-sided *t*-test with a nominal significance level of  $\alpha = .10$ . The proposed sequencing is based on the assumption that the effect of oxybutynin will increase monotonically with respect to dose. If p < .10 for both tests, we will conclude that both dosing schedules significantly improved hot flash scores at 6 weeks relative to placebo. If  $p \le .10$  for the first test but p > .10 for the second test, we will conclude that the higher dosing schedule significantly improved hot flash scores at 6 weeks relative to placebo but that the lower dosing schedule did not significantly improve hot flash scores at 6 weeks relative to placebo. Finally, if p > .10 for the first test, we will conclude that neither dosing schedule significantly improved hot flash scores at 6 weeks relative to placebo. In practice, if p > .10 for the first test, we will still conduct the second test, but as an exploratory analysis rather than as a primary analysis. We will also conduct a responder analysis at 6 weeks comparing the proportion of patients who experience a clinically significant improvement in hot flash scores since baseline across the oxybutynin and placebo arms using Fisher's exact test,  $\chi^2$  test, or logistic regression. Stratification factors used in the randomization as well as baseline patient characteristics and prognostic factors may be included in the logistic regression model as covariates if imbalances across arms occur. A clinically significant improvement will be defined as a 50% or greater reduction in hot flash scores since baseline based on preliminary evidence suggesting that patients consider a 50% or greater reduction in frequency of moderate to severe hot flashes to be a meaningful improvement.[41, 42] Patients who experience a 50% or greater reduction in hot flash scores since baseline will be deemed responders, while the remaining patients (including those with missing hot flash scores) will be deemed non-responders. As an exploratory analysis, we will investigate whether these efficacy results differ when using a single day rather than a full week to define patients' baseline hot flash scores.

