#### 13.5 Sample Size and Power

As this is a pilot trial, the sample size was determined based on feasibility and logistical considerations rather than on power for hypothesis testing. We aim to enroll 26 evaluable patients per oxybutynin arm and 13 evaluable patients per placebo arm (i.e., 78 evaluable patients total). For the primary aim, 26 evaluable patients per oxybutynin arm and 13 evaluable patients per placebo arm with 6 weekly hot flash scores provide 76% power to detect a mean difference in hot flash score reduction from baseline when comparing each oxybutynin arm (5.0 mL twice daily or 2.5 mL twice daily to the placebo arm (both placebo arms combined) based on a two-sided *t*-test estimated via a mixed model, nominal significance level of  $\alpha = .10$ , intraclass correlation of .50, and population standardized mean difference of 0.50 (i.e., Cohen's convention for a moderate effect size)[44]. In a similar study in women, Cohen's *d* equaled 0.85 when comparing the higher dose oxybutynin arm (2.5 mL twice daily escalated to 5.0 mL twice daily) to the placebo arm [45]. An additional 9 patients will be accrued to account for a 10% loss in sample size due to ineligibility, major treatment violation, or cancellation. Maximum projected accrual is, therefore, 87 patients.

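### Section 13.4 admits the three minimization factors to the primary model only at discretion, on an undefined imbalance. If they predict change and arm variances are similar, omitting them makes the week-6 test conservative and forgoes a few points of power

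*Combined protocol and SAP*

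**What the plan says.** Section 4.5.2 states that "the patient will be assigned to one of the following treatment groups using the Pocock and Simon dynamic allocation procedure". The factors, listed in 4.5.1 and again in 13.2, are daily hot flash frequency, hot flash duration and number of prior hot flash therapies, each in two levels.

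The primary model in 13.4 has baseline and the six weekly scores as responses, with an intercept, nominal time, arm and their interaction as fixed effects. The stratification factors, together with other baseline characteristics and prognostic factors, "may be included in the mixed model as covariates if imbalances across arms occur". For the responder analysis the same group of variables "may be included in the logistic regression model as covariates if imbalances across arms occur". Neither sentence says what counts as an imbalance, who decides and when, or whether the factors would enter as main effects or by week.

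The covariance is also left partly open: "Alternative structures will be investigated for the residual covariance matrix", with the choice made on convergence and the Akaike criterion. The tested quantity is the difference between arms in change from baseline to week 6, at two-sided 0.10, high dose first and then low dose. On size, 13.5 says that "the sample size was determined based on feasibility and logistical considerations rather than on power for hypothesis testing".

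**The concern.** Minimization makes the arms alike on these factors, so it removes most of their effect from the difference between arms. If the model then omits them, that effect stays in the residual. The model standard error is larger than the true sampling error of the contrast, and the test runs below its nominal level. The entry condition asks about the very property that the allocation is built to secure, and even when it is met, inclusion stays optional.

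What is at stake is precision, in a comparison of 26 with 26 patients, and a primary model whose covariates are not fixed in advance. Because the formal low-dose test depends on the high-dose test being significant, power lost on the first test affects both.

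**Working it through.** **The plan's figure.** Inputs from 13.5: 26 against 26 (pooled placebo), two-sided 0.10, intraclass correlation 0.50, standardized difference 0.50, six weekly scores. The variance of a six-week mean is (1 + 5 × 0.5)/6 = 0.583, so its SD is 0.764. The standard error of the difference is 0.764 × √(2/26) = 0.212. Power = Φ(0.50/0.212 − 1.645) = 0.763, the stated 76%. It applies to the average over six weeks. For the week-6 change, the variance is 2 × (1 − 0.5) = 1, the standard error is √(2/26) = 0.277, and power = Φ(0.50/0.277 − 1.645) = 0.563. Gains from adjustment should be read against this second figure. The mismatch between the two is a separate matter.

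**Closed form.** Let R² be the share of variance in week-6 change explained by the three factors. With perfect balance and normal data, omission inflates the model standard error by 1/√(1 − R²), so the effective critical value is 1.645/√(1 − R²): 1.69, 1.73 and 1.84 at R² = 5%, 10% and 20%. The true sizes are 0.091, 0.083 and 0.066.

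**Simulation.** N = 78 allocated 2:2:1:1 by minimization, placebo pooled, complete normal data, equal arm variances, d = 0.5 on the change scale. Assumed, because the documents do not give them: assignment probability 0.7 to 0.9, factor prevalences 0.4/0.5/0.4, equal factor effects, and R² itself.

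| R² | Size, factors omitted | Size, factors by week | Power change from adjusting (points) |
|---|---|---|---|
| 0 | 0.097–0.102 | 0.097–0.102 | −0.4 to 0 |
| 5% | 0.091–0.095 | 0.097–0.102 | +1.4 to +1.6 |
| 10% | 0.080–0.087 | 0.097–0.102 | +3.3 to +3.4 |
| 20% | 0.067–0.072 | 0.097–0.102 | +7.3 to +7.6 |

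At assignment probability 0.8, power goes from 0.550 to 0.565, 0.550 to 0.583 and 0.551 to 0.627 at 5%, 10% and 20%. Under simple randomization the unadjusted size stays near 0.10, so the conservatism comes from minimizing and then not adjusting.

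**Form of entry.** Baseline is a response in this model. With complete data and unstructured or compound-symmetry covariance, time-constant main effects cancel from the change contrast: the estimate is the same and the standard-error ratio is 1.000. In unstructured REML fits with 10% dropout at R² = 10%, the mean standard error was 0.3021 with no factors, 0.3018 with main effects and 0.2878 with factor-by-week terms. Power was 0.515, 0.517 and 0.573 (simulation error 2 to 3 points each, less on paired differences). Under AR(1) with complete data, where the factors also shifted the level by 0.5 SD, main effects moved the mean standard error from 0.369 to 0.341. What main effects do therefore depends on dropout and on the covariance structure selected.

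**How often the condition is met.** With a spread between arms above 10 percentage points as the rule and assignment probability 0.8, it is met in about 25% of trials when exactly 78 are minimized. It is met in about 55% when 87 are minimized and 9 removed at random, which is closer to 13.2 and 13.5. With chi-square p < 0.10 as the rule and 78 minimized, it is met in 0.02 to 0.55% over assignment probabilities 0.7 to 0.9.

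**Unequal variances.** Section 1.2 gives change SDs in women of 15.6 (5.0 mg), 7.7 (2.5 mg) and 10.2 (placebo). Pooled over three equal arms: √[(15.6² + 7.7² + 10.2²)/3] = 11.64. The 5.0 mg contrast needs √[(15.6² + 10.2²)/2] = 13.18, so a common matrix makes its standard error about 12% too small. In simulation at R² = 10%, non-coverage of the nominal 90% interval was 13.0% without and 15.0% with the factors.

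**The case against.** **The factors may not be prognostic.** This stands. R² is not in the documents. The stratum value is recorded for allocation, whereas "The baseline symptoms determination is completed after registration and randomization but prior to initiation of study treatment", so the frequency stratum is not a split of the diary baseline. At R² = 0 nothing is lost. If baseline score were itself a covariate, which 13.4 does not plan, the factors would add −0.5 to +1.2 points at 10% and −0.3 to +3.5 at 20%, assuming that the frequency factor explains 49% of baseline-score variance.

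**The figures compare never with always adjusting, and the plan does neither.** This also stands. With 87 minimized and 9 removed, adjusting only when the spread exceeds 10 points gave size 0.092 at R² = 10%, against 0.085 for never adjusting. The conditional rule lies in between, at a place set by a threshold that the plan does not state. A reader might infer that the condition would almost never be met. The documents do not support that, because exclusions after allocation loosen the balance and some plausible thresholds are met often.

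**The intervals need not over-cover.** A reader might infer that the 90% intervals are always too wide. That holds only with similar arm variances. With the SDs in 1.2 and a common matrix, the 5.0 mg interval under-covers with or without the factors, and adjusting moves it further from 90%. Those SDs come from women on treatment, and the 2.5 mg contrast goes the other way (it needs 9.04). This is a separate issue about the covariance model, not a reason to omit the factors.

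**The larger model may not fit.** Mean parameters rise from 21 to 42. All 2,300 simulated unstructured fits converged, but on normal data. Skewed diary data may need a simpler structure, which 13.4 already allows.

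**No calculation supports the logistic part.** True. It is proposed for consistency only.

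**Conclusion.** The point holds as a modest, nearly free improvement. Given prognostic factors, similar arm variances and minimization as described, omitting the factors gives a true level of about 0.09 at R² = 5 to 10% and 0.07 at 20%. It forgoes about 1.5, 3.3 and 7.5 points of power at 5%, 10% and 20% relative to always adjusting. The plan's conditional rule loses less than that, by an amount that cannot be fixed without a threshold.

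Two stronger readings are not supported. Omitting the factors does not raise the false-positive rate; its effect is conservative. Nor does it contradict the 76% in 13.5, which reproduces on its own inputs in a section that rests the sample size on feasibility.

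**What to change.** In 13.4, for the three stratification factors only, remove the imbalance condition. State that they are always in the primary mixed model with factor-by-week terms, and that time-constant main effects alone are not relied on. Include them as main effects whenever logistic regression is used for the responder analysis.

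Name any other baseline covariates before the first patient is unblinded, or otherwise in a dated plan written without access to outcomes by arm. A general reference to unblinding would not serve as a milestone, because 4.7, 7.3 and 8.3.2 unblind patients one at a time after six weeks.

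The cost is two or three sentences and about three degrees of freedom at the week-6 contrast (75 to 72). If the factors are not prognostic, the power cost was 0 to 0.4 points with complete data; allow up to about one. A simpler covariance structure may be needed if the larger model does not converge. No patient, visit or drug procedure changes.

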#### 7.1 Baseline Symptom Documentation

The patient will be instructed not to take any study medication for the first seven days of the study, but to complete their daily questionnaires (Baseline Symptom Documentation – Appendix II) during this baseline period. At the end of the week, patients will complete Symptom Experience Questionnaire (Appendix V) and Hot Flash Related Daily Interference Scale (Appendix VI).

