#### 9.2 CTCAE Routine Reporting Requirements

The following table outlines the combinations of time points, grades and attributions of AEs that require routine reporting to the Alliance Statistics and Data Center. Questions about routine reporting should be directed to the Data Manager.

Combinations of CTCAE Grade & Attribution Required for Routine AE Data Submission on Case Report Forms (CRFs)

Attribution	Grade 1	Grade 2	Grade 3	Grade 4	Grade 5
Unrelated			а	а	а
Unlikely			a	a	a
Possible		a	a, b	a, b	a, b
Probable		a	a, b	a, b	a, b
Definite		а	a, b	a, b	a, b

- a) Adverse Events: Other CRF Applies to AEs occurring between registration and within 30 days of the patient's last treatment date, or as part of the Clinical Follow-Up Phase.
- b) Adverse Events: Late CRF Applies to AEs occurring greater than 30 days after the patient's last treatment date.

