#### Follow-up for ineligible patients who continue with protocol treatment

Patients who are deemed ineligible after registering may continue protocol treatment, provided the treating physician, study chair, and executive officer agree there are no safety concerns if the patient continues protocol treatment. All scans, tests, and data submission are to continue as if the patient were eligible. Notification of the local IRB may be necessary per local IRB policies.

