#### Follow-up for patients who are registered, but who never start study treatment

For all study participants who are registered to the trial but who never receive study intervention (regardless of eligibility), the follow-up requirements are specified below:

Baseline and off-treatment notice data submission required. See the Data Submission Schedule accompanying the All Forms Packet.

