#### 13.2 Study Design

Patients will be randomly assigned to oxybutynin at 2.5 mL twice daily, oxybutynin at 5.0 mL twice daily, placebo at 2.5 mL twice daily, or placebo at 5.0 ml twice daily in a 2:2:1:1 ratio according to the dynamic allocation scheme. Stratification factors will include daily hot flash frequency at baseline (4 to 9 hot flashes per day versus 10 or more hot flashes per day), hot flash duration at baseline (less than 9 months versus 9 or more months), and number of prior hot flash therapies (0 versus 1 or more). The study design includes two placebo arms to match the dose of the two oxybutynin arms; however, patients randomized to the two placebo arms will be combined to form a single placebo arm for analysis. All analyses will follow an intent-to-treat approach that includes all randomized patients who meet eligibility criteria.

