
Weekly hot flash frequencies (as opposed to weekly hot flash scores) will be compared across the oxybutynin and placebo arms in a manner similar to above using a mixed model that accounts for the observed distribution of weekly hot flash frequencies. A fixed sequence procedure will be employed. For the responder analysis, patients who experience a 50% or greater reduction in hot flash frequency since baseline will be deemed responders, while the remaining patients (including those with missing hot flash frequencies) will be deemed non-responders. Finally, consistency of the results will be assessed across the various methods used to evaluate the efficacy of oxybutynin in this trial (i.e., hot flash scores versus hot flash frequencies, mean differences versus 50% or greater reduction since baseline, single day versus full week to define patients' baseline hot flash scores).

**To assess safety**, the proportion of patients experiencing a grade 3 or higher adverse event will be summarized by arm. We expect this proportion to be extremely low for all arms.

To assess tolerability, mixed models similar to the one described above will be estimated that include baseline and weekly patient-reported symptoms as measured by the Symptom

Experience Questionnaire (Appendix V) across the 6-week treatment period. A single mixed model will be developed for each patient-reported symptom. Estimates from the mixed models will be used to construct 90% confidence intervals for mean differences in patient-reported symptoms between the oxybutynin and placebo arms (i.e., Arm A versus Arms C and D combined; Arm B versus Arms C and D combined) at 6 weeks post-randomization. Contrasts estimated via the mixed models will involve a two-sided *t*-test with a nominal significance level of  $\alpha = .10$ .

**To assess feasibility**, the time required to accrue 87 patients will be reported. To move forward with a phase III trial, an average accrual rate of 4 patients per month (starting 4 months after enrollment begins, to account for the time required for multiple institutions to activate the trial) would be desired. The treatment adherence rate (i.e., the number of patients who completed treatment per protocol divided by the number of patients who started treatment) will be summarized by arm.

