#### **13.7.1** Adverse Event Stopping Rules

The stopping rules specified below are based on the knowledge available at study development. We note that the adverse event stopping rule may be adjusted in the event of either (1) the study re-opening to accrual or (2) at any time during the conduct of the trial and in consideration of newly acquired information regarding the adverse event profile of the treatment(s) under investigation. The study team may choose to suspend accrual because of unexpected adverse event profiles that have not crossed the specified rule below.

Accrual will be temporarily suspended to this study if at any time we observe adverse events considered at least possibly related to study treatment (i.e., an adverse event with attribute specified as "possible", "probable", or "definite") that satisfy either of the following:

- if 2 or more patients in the first 10 treated patients experience a grade 3 or higher adverse event felt to be attributed to the study agent and the event rate is higher in the treatment arms than the placebo arm.
- if after the first 10 patients have been treated, 10% of all patients experience a grade 3 or higher adverse event felt to be attributed to the study agent and the event rate is higher in the treatment arms than the placebo arm.

We note that we will review grade 4 and 5 adverse events deemed "unrelated" or "unlikely to be related," to verify their attribution and to monitor the emergence of a previously unrecognized treatment-related adverse event.

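### The grade 3 or higher adverse event proportion is set on eligible randomized men, so it omits treated men later found ineligible and counts men who never took a dose

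*Combined protocol and SAP*

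**What the plan says.** - **Population.** Section 13.2, repeating 13.1: "All analyses will follow an intent-to-treat approach that includes all randomized patients who meet eligibility criteria". Section 13.1 names safety together with efficacy as what the trial assesses.
- **Safety summary.** Section 13.4: "the proportion of patients experiencing a grade 3 or higher adverse event will be summarized by arm". The plan expects this proportion to be extremely low in every arm. The paragraph gives no population, onset window or attribution limit of its own.
- **Men found ineligible after registration.** Section 12.5: "Patients who are deemed ineligible after registering may continue protocol treatment", if the treating physician, study chair and executive officer see no safety concern. Their data submission goes on as for eligible men. Those who start and then stop submit what an eligible man who stops would submit.
- **Men who never start.** Section 12.5: "Baseline and off-treatment notice data submission required". It points to a Data Submission Schedule that is not part of the documents.
- **Timing.** The baseline form is "completed after registration and randomization but prior to initiation of study treatment" (Section 11.1), and "The patient will be instructed not to take any study medication for the first seven days of the study" (Section 7.1). The routine adverse event form in Section 9.2 "Applies to AEs occurring between registration and within 30 days of the patient's last treatment date", with grade 3 or higher reported whatever the attribution.
- **Other denominators.** Adherence (13.3 and 13.4) is divided by the men who started treatment. In 13.7.1 the first accrual-suspension bullet reads "if 2 or more patients in the first 10 treated patients experience" a grade 3 or higher event. The second applies a 10% limit to all patients and does not repeat the word treated.

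**The concern.** An intent-to-treat set restricted to eligible men can be argued for in the efficacy analysis. It does not suit a summary of what happened to men who took the drug. Applied to adverse events, the rule works in two directions:

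- It removes exposed men. A man who was dosed and later ruled ineligible contributes neither his event nor himself. Section 3.2.6 describes several of its exclusions as contraindications to oxybutynin, so some of these men could bear directly on secondary objective 2.2.2, the safety profile.
- It retains unexposed men. Randomization comes before a week without study drug, so a man can cancel before his first dose and still be in the denominator, with little follow-up asked of him.

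At stake is the accuracy of the one planned adverse event proportion per arm, in groups small enough for a single man to change it visibly.

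**Working it through.** **1. Group size, from the plan's own figures (Section 13.5).** Evaluable: 26 + 26 + 13 + 13 = 78. Allowing 10% loss, 78/(1 - 0.10) = 86.7, rounded up to 87, which reproduces the stated maximum accrual. With 2:2:1:1 allocation and the placebo arms pooled, each comparison group has 87/3 = 29 men. The allowance for ineligibility, major treatment violation and cancellation together is 87 - 78 = 9 men (9/87 = 10.3%).

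**2. Who is in the set.**

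| Man | Set as written (randomized and eligible) | Set of men who took a dose |
|---|---|---|
| Eligible, dosed | in | in |
| Ineligible, dosed | out | in |
| Eligible, never dosed | in | out |
| Ineligible, never dosed | out | out |

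The two sets differ in the second and third rows.

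**3. Treated ineligible man.** The documents give no counts of such men or of events, so these are illustrations for one group of 29, all dosed, with one man ineligible.

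- He has the group's only event: dosed set 1/29 = 3.4%; set as written 0/28 = 0%.
- He has an event and two eligible men do too: 3/29 = 10.3% against 2/28 = 7.1%.
- He has no event and two eligible men do: 2/29 = 6.9% against 2/28 = 7.1%.

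The figure moves by about 3 points only if he has an event.

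**4. Never-dosed men.** Assume three of 29 are never dosed, all three are eligible, and they have no recorded event.

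- One event: dosed set 1/26 = 3.8%; set as written 1/29 = 3.4%.
- Two events: 2/26 = 7.7% against 2/29 = 6.9%.

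Three such men in each of three groups would use all 9 men of the allowance, so this is the upper end of what the plan budgets for.

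**5. Drug-free week.** Days 1-7 are 7 of 49 study days (14.3%), or 7 of 49 + 30 = 79 days of the Section 9.2 window (8.9%). One grade 3 or higher event in that week, if counted, adds 1/29 = 3.4 points to a group, for example from 2/29 = 6.9% to 3/29 = 10.3%.

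**6. Power.** The stated 76% rests on the hot flash score comparison and not on the safety set. With six weekly scores and intraclass correlation 0.50, the SD of the mean score is sqrt((1 + 5 x 0.50)/6) = 0.764. With 26 per group, difference 0.50 and two-sided alpha 0.10, power is 76.3%. The stated figure reproduces, and a change of safety set leaves it alone.

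**The case against.** The strongest reply is that little is at risk. The 13.4 safety summary is descriptive, with no test, interval or phase III threshold attached. Treated ineligible men still submit their data, expedited reporting applies, and the monitoring board reviews safety at least twice a year. All of this stands. The fault is in the final summary and not in data capture or oversight.

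Some stronger readings are tempting, and the documents do not support them.

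- *A reader might infer that the safety table counts the drug-free week.* Section 9.2 says which events go on a form. It does not set an analysis window, and the study calendar places the adverse event call only at the end of each treatment week. What can be said is that nothing excludes those events.
- *A reader might infer that never-dosed men are certainly scored as event-free.* Section 13.5 treats cancellation as a loss from the evaluable number, and the Data Submission Schedule is not available. The written rule keeps these men in the denominator; how their events would be recorded is not settled.
- *A reader might infer that 13.7.1 works throughout on treated men.* Only its first bullet says so. Both bullets are limited to events at least possibly related to treatment, a limit that 13.4 does not have.
- *A reader might infer that one man decides the arm comparison, or that the omitted men are the most informative for safety.* Nothing is decided by a descriptive proportion. Ineligibility could also rest on hot flash frequency, stability of hormone therapy or language.

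None of this answers the population point. An unwritten habit of using treated patients does not help when the written rule covers all analyses.

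**Conclusion.** The point holds for the analysis population. As written, Sections 13.1, 13.2 and 13.4 give an adverse event proportion that drops treated men later found ineligible and keeps eligible men who never took a dose. The first effect matters more: one event in such a man separates 1/29 (3.4%) from 0/28, so an arm's only event could go unreported in this summary. The second is small, about 0.4 points with one event and three never-dosed men.

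The Days 1-7 effect is an inference from the absence of an onset rule. Since that week follows randomization, such events would fall on the arms by chance.

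These sizes assume 29 men per group and hypothetical counts of events and of affected men. The plan's only bound is 9 men for three causes combined, and a major treatment violator need be neither undosed nor ineligible. The point is worth correcting before analysis, and it does not threaten the trial's main conclusion.

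**What to change.** **Section 13.4, safety paragraph.** Exempt the adverse event summary from the rule in 13.1 and 13.2. Define its set as all men who took at least one dose of study product, whatever their eligibility, grouped by the product received in the blinded period. Count events with onset from the first dose, and list Days 1-7 events separately.

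**Section 13.7.1.** State the same treated denominator in both bullets, since the first names treated patients and the second does not.

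**Unchanged.** Leave the population for the patient-reported tolerability models as it is; no fault is shown there.

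**Cost.** A change of wording and a little extra analysis work. Section 12.5 already requires data from treated men whatever their eligibility. The case report forms are not in the documents, so check that they carry event onset and first-dose dates. Sample size (87) and power (76%) do not change.
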